8.1.1. Baseline Procedures

All procedures listed in the SoA must be conducted at this visit.

SoA must be conducted at the screening visit.

8.2. Efficacy Assessments

Efficacy parameters are not evaluated in this study.

8.3. Safety Assessments

Planned time points for all safety assessments are provided in the SoA. Unscheduled safety measurements may be obtained at any time during the study to assess any perceived safety issues.

8.3.1. Physical Examinations

A complete physical examination will include, at a minimum, head, ears, eyes, nose, mouth, skin, heart and lung examinations, lymph nodes, and gastrointestinal, musculoskeletal, and neurological systems.

A brief physical examination will include, at a minimum, assessments of general appearance, the respiratory and cardiovascular systems, and participant reported symptoms.

Complete physical examination must either be conducted at screening or upon admission on Day -1 only; targeted physical examination may be performed as appropriate at the investigator's discretion if there are findings during the previous examination, new/open adverse events.

Physical examinations may be conducted by a physician, trained physician's assistant, or nurse practitioner as acceptable according to local regulation.

Ophthalmologic examination, including fundoscopy, will be conducted by an ophthalmologist at baseline (Screening) and for clinical monitoring of any signs or symptoms throughout the trial, as needed.

Height and weight will also be measured and recorded as per the SoA. For measuring weight, a scale with appropriate range and resolution is used and must be placed on a stable, flat surface. Participants must remove shoes, bulky layers of clothing, and jackets so that only light clothing remains. They must also remove the contents of their pockets and remain still during measurement of weight.

Physical examination findings collected during the study will be considered source record and will not be required to be reported, unless otherwise noted. Any untoward physical examination findings that are identified during the active collection period and meet the definition of an AE or SAE (Appendix 3) must be reported according to the processes in Sections 8.4.1 to 8.4.3.

8.3.2. Vital Signs

Vital signs (BP, PR and temperature) will be collected at times specified in the protocol SoA.

8.3.2.1. Blood Pressure and Pulse Rate

At screening, vital signs will be measured using standard methodology. Supine BP will be measured with the participant's arm supported at the level of the heart, and recorded to the nearest mm Hg after approximately 5 minutes of rest. The same arm (preferably the dominant arm) will be used throughout the study. Participants should be instructed not to speak during measurements. The use of an automated device for measuring BP and pulse rate is acceptable; however, when done manually, pulse rate will be measured in the brachial/radial artery for at least 30 seconds.

During periods 1 and 2, ambulatory BP and PR will be monitored using the BioBeat chest-monitor, a single-participant-use device and web-enabled management platform either (1) at the CRU by the CRU staff and/or by study participants or (2) remotely by the study participants, as specified in the protocol SoA. Investigational site staff and study participants will be provided training as well as the BioBeat user manual.

When the timing of these measurements coincides with a blood collection, BP and pulse rate should be obtained prior to the nominal time of the blood collection. Additional collection times, or changes to collection times, of BP and pulse rate will be permitted, as necessary, to ensure appropriate collection of safety data.

Any untoward vital sign findings that are identified during the active collection period and meet the definition of an AE or SAE (Appendix 3) must be reported according to the processes in Sections 8.4.1 to 8.4.3.

8.3.2.2. Temperature

Temperature will be measured orally. No eating, drinking, or smoking is allowed for 15 minutes prior to the measurement.

8.3.3. Electrocardiograms

Electrocardiograms (except at screening) will be obtained using the PCA 500 which is a wearable ECG monitor. The PCA500 provides 12-lead ECG monitoring and recording which is transmitted periodically at pre-specified time intervals. Investigational site and study participant training are supplemented by availability of the PCA500 user manual.

At screening, standard 12-lead ECGs will be collected to assess and quantify HR, PR, QT, QTcF, and QRS intervals. During Periods 1 and 2, ECGs will be collected using the PCA500 wearable monitoring device, at the times specified in the protocol SoA, either (1) at the CRU by the CRU staff or by the study participant or (2) remotely by the study participant.

All scheduled ECGs should be performed after the participant has rested quietly in a supine position or in the most recumbent position possible for at least 5 minutes.

The pre-etrasimod dose 12-lead ECGs will be done in triplicate. Triplicate 12-lead ECGs will be obtained approximately 5 minutes apart; the average of the triplicate ECG measurements collected pre-etrasimod dose on Day 1 of each period will serve as each participant's baseline QTcF value.

To ensure safety of the participants, a qualified individual at the investigator site will make comparisons to baseline measurements from the current period. Additional ECG monitoring will occur if a) the mean value from the triplicate measurements for any postdose QTcF interval remains ≥60 ms from the baseline and is >450 ms; or b) an absolute QTcF value is ≥500 ms for any scheduled ECG for greater than four hours (or sooner, at the discretion of the investigator); or c) QTcF values get progressively longer. If any of these conditions occurs, then a single ECG measurement must be repeated at least hourly until QTcF values from 2 successive ECGs fall below the threshold value that triggered the repeat measurement.

In some cases, it may be appropriate to repeat abnormal ECGs to rule out improper lead placement as contributing to the ECG abnormality. It is important that leads be placed in the same positions each time in order to achieve precise ECG recordings. If a machine-read QTc value is prolonged, as defined above, repeat measurements may not be necessary if a qualified medical provider's interpretation determines that the QTcF values are in the acceptable range. Please refer to Section 7.1.2 for guidance on QTcF changes management.

ECG values of potential clinical concern are listed in Appendix 7.

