12-Lead ECG	X		X	X	X		X	 Assessments using standard ECG machine at screening. Assessments using wearable device for Periods 1 and 2. On Day 1 of each period perform ECGs pre-etrasimod dose and every hour up to 6 hours, and at 8 and 24 hours post-etrasimod dose (in Period 1 by staff and in Period 2 by participants). The pre-etrasimod dose ECGs will be done in triplicate. On Days 3-5 of each period, perform ECGs at approximately the same clock time as etrasimod dose on Day 1 (in both Periods by participants). Refer to Section 8.3.3 for additional details
Blood pressure, pulse rate, temperature	X		X	X	X		X	 Assessments using standard methodology (BP, PR and temperature) at screening. Assessments using standard methodology (temperature) in Periods 1 and 2. Temperature will only be performed predose on Day 1.

 Table 1.
 Study Schedule of Assessment

Visit Identifier Abbreviations used in this table may be found in Appendix 10	Screen		Peri	iods 1-2		F/U Telephone Contact	ЕТ	Notes
Days Relative to Day 1 in Each Period	Day -28 to Day -2	Day -1	Day 1	Day 2	Days 3-8	Days 28-35*		 Participants will be screened within 28 days of the first dose of study intervention. * Follow-up contact will occur by telephone and must occur at least 28 to 35 days after the last administration of etrasimod (Day 1 of Period 2 if dosing completed).
Period 1 Study Days	-28 to -2	-1	1	2	3-8			Participants will be discharged from CRU on Day 2 of Period 1
Period 2 Study Days		9	10	11	12-17			 Minimum 8-day washout period between dosing in Periods 1 and 2 Participants will be discharged from CRU on Day 2 of Period 2.
HIV, HbsAg, HbcAb, HbsAb, HCVAb	X							Assessments using wearable device (BP, PR) in Periods 1 and 2. On Day 1 of each period PR and BP vital signs will be performed at predose (baseline) and every hour up to 6 hours, and at 8 and 24 hours post-etrasimod dose (in Period 1 by CRU staff and in Period 2 by participants). On Days 3-5 of each period, PR and BP will be taken at approximately the same clock time as etrasimod dose on Day 1 (in both Periods by participants). ECG will be taken first followed by vital signs. If HbsAg is negative and HbcAb is positive,
COVID-19 related procedures		X						HbsAb should be evaluated. • Performed per local procedures
TB (QuantiFERON® Gold Test)	X							- Terrormed per rocal procedures

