7.1.2. ECG Changes

Participants must permanently discontinue study intervention if suspected intolerance associated with first dose cardiac effects (Section 2.3.1).

If an ECG shows a new onset QTc interval above 500 ms during the treatment period, a repeat ECG is warranted. If this abnormal finding is confirmed, study intervention must be interrupted. Effective diagnostic and therapeutic strategies should be employed.

Reversible causes of prolonged QTc interval (eg, electrolyte abnormalities or hypomagnesemia), should be corrected as clinically indicated. When evaluating a participant with new onset QTc interval above 500 ms, referral to a cardiologist experienced in treating cardiac conduction disorders should be considered. Re-initiation of study treatment can only be considered after all of the following have occurred:

- The QTcF interval is <450 ms (males) or <470 ms (females),
- The QTc prolongation is considered by the investigator and confirmed by the cardiologist as not related to study treatment and likely caused by other factors,
- Individual risk-benefit is favorable (as determined by the investigator, in agreement with the cardiologist), and
- After discussion with the Medical Monitor.

If a clinically significant finding is identified (including, but not limited to, changes from baseline in QTcF after enrollment), the investigator or qualified designee will determine if the participant can continue in the study and if any change in participant management is needed. This review of the ECG printed at the time of collection or acquired using wearable monitoring device must be documented. Any new clinically relevant finding should be reported as an AE.

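### Limb (a) of the additional-ECG rule tests a postdose triplicate mean, but triplicate ECGs are specified only before dosing

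*Protocol*

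**What the plan says.** Protocol Section 8.3.3 lists three conditions, any one of which requires additional ECG monitoring:

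- (a) "the mean value from the triplicate measurements for any postdose QTcF interval remains" at least 60 ms above baseline and is also above 450 ms;
- (b) an absolute QTcF of at least 500 ms lasting more than four hours, or sooner if the investigator so decides;
- (c) QTcF values that become progressively longer.

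If any of these occurs, "then a single ECG measurement must be repeated at least hourly until QTcF values from 2 successive ECGs fall below the threshold value" that set off the repeats. A later sentence relaxes this for a prolonged machine-read value: "repeat measurements may not be necessary if a qualified medical" provider reads the QTcF as acceptable.

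On replication, the 12-lead ECG row of the Schedule of Activities (Section 1.3) says "The pre-etrasimod dose ECGs will be done in triplicate". It gives no replicate number for any postdose ECG. Section 8.3.3 likewise calls for triplicates before dosing and makes their average the baseline for the period. SAP Section 3.2.2.5 uses the triplicate average only as baseline and defines no averaging of postdose values.

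On timing, the same row says, for Day 1 of each period, "perform ECGs pre-etrasimod dose and every hour up to 6 hours, and at 8 and 24 hours post-etrasimod dose". It adds: "On Days 3-5 of each period, perform ECGs at approximately the same clock time as etrasimod dose on Day 1". The Day 3 to 5 ECGs are done by the participant after discharge.

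**The concern.** Limb (a) is the only limb with a numeric change-from-baseline criterion, and it is written on a quantity that the schedule does not produce. The word *remains* may hint at a confirmatory set, but no text says what would prompt one or when it would be taken.

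At stake is the mandatory character of the hourly repeat. A participant could show a QTcF rise of 60 ms or more to above 450 ms without meeting (b) or (c), and the text as written would then not require repeats. What is lost is the default to repeat when the qualified provider does not judge the value acceptable. This matters most where the next scheduled ECG is hours away or where the participant is at home.

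**Working it through.** The plan states no figure on this point. The check sets the texts side by side and counts schedule slots.

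**1. Is a postdose triplicate specified anywhere?**

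| Place | What it specifies |
|---|---|
| Protocol 1.3, ECG row | Triplicate before dosing; no replicate number after dosing |
| Protocol 8.3.3 | Triplicate before dosing, about 5 minutes apart, averaged for baseline |
| Protocol 5.2, exclusion 14 | ECG repeated twice and three values averaged, for eligibility only |
| Protocol 7.1.2 | "If an ECG shows a new onset QTc interval above 500 ms during the treatment period, a repeat ECG is warranted" (one repeat, not a triplicate) |
| SAP 3.2.2.5 | Triplicate average as baseline only |

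None supplies the input to limb (a). Exclusion 14 shows that the protocol spells out a confirmatory set of three where it wants one.

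**2. Scheduled postdose ECG times per period.** 1, 2, 3, 4, 5, 6, 8 and 24 h (8 times) plus Days 3, 4 and 5 (3 times, at about 48, 72 and 96 h): 8 + 3 = 11. Times with a specified triplicate: 0 of 11.

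**3. Gap to the next scheduled ECG in the period.**

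| ECG time | Next scheduled ECG |
|---|---|
| 1 to 5 h | 1 h later |
| 6 h | 2 h later |
| 8 h | 16 h later |
| 24 h | 24 h later |
| Day 3, Day 4 | 24 h later each |
| Day 5 | none |

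At 6 of 11 times (6 h, 8 h, 24 h, Days 3, 4 and 5) no further ECG is due within 1 h, so the schedule itself does not stand in for the hourly repeat. Three of those 6 (Days 3 to 5) are remote. These are schedule slots, not expected events.

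**4. Do limbs (b) and (c) cover the same case?** Both can be applied to single ECGs, but they test different things. An illustrative path, with assumed values: baseline 390 ms, 8 h 388 ms, 24 h 460 ms, Day 3 458 ms.

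- Change at 24 h: 460 − 390 = 70 ms, and 460 > 450. The figures in (a) are met.
- Change on Day 3: 458 − 390 = 68 ms, and 458 > 450. Met again.
- Limb (b): no value reaches 500 ms. Not met.
- Limb (c): one step up, then a plateau. Not met if that does not count as progressive lengthening, a term the protocol does not define.

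A gradual rise across the hourly ECGs, by contrast, might well be caught by (c).

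**5. Does it matter which reading a site adopts?** Assume replicate errors are independent with equal variance σ². A single postdose value minus a triplicate-mean baseline has error variance σ² + σ²/3 = 4σ²/3. A triplicate mean minus a triplicate-mean baseline has σ²/3 + σ²/3 = 2σ²/3. The SD ratio is √(4/3 ÷ 2/3) = √2 ≈ 1.41. The two readings need not trigger at the same rate, so the text should settle which one applies.

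**The case against.** The best answer is that the intent is clear and the consequence small. The waiver sentence in Section 8.3.3 speaks of a single prolonged machine-read value and assumes that repeats are the default, so a site would probably apply limb (a) to the single postdose value. Section 8.3.3 also requires a qualified person at the site to compare ECGs with the current period's baseline, with no restriction to triplicates, so a rise of this size should be looked for. Appendix 7 lists nearly the same criterion (above 450 ms with a change of more than 60 ms) as a possible SAE, without a triplicate. Section 7.1.2 requires a documented decision on clinically significant findings, Section 8.3 allows unscheduled measurements, and Section 10.3.3 obliges medically indicated follow-up of an AE.

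The slot count in step 3 would be the same under perfect wording, and the path in step 4 was chosen to escape limb (c). Nothing in the documents makes it likely: fasted median Tmax is about 4 h (Section 2.2.4.1), and Section 2.2.3 reports increases in hERG current, not inhibition.

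Most of this stands. It shows the probable intent and softens the consequence. But none of these provisions supplies the mandatory at-least-hourly repeat for the affected case. The comparison with baseline finds the value without saying what must follow, and the waiver removes a repeat without triggering one. The other provisions are permissive or depend on clinical judgement.

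**Conclusion.** The inconsistency holds. Taken literally, limb (a) cannot be evaluated at any of the 11 scheduled postdose ECG times in a period. The gap is confined to QTcF rises of at least 60 ms to above 450 ms that are not progressively lengthening and do not meet (b). No upper QTcF limit is put on that range, because (b) also requires persistence beyond four hours unless the investigator acts sooner; above 500 ms, Section 7.1.2 separately calls for a repeat.

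Severity is minor. The documents give no frequency for such rises, and there may be none in 8 participants. Other safeguards remain, and neither the PK analysis nor the SAP QTcF tables depend on this rule. The slot count rests only on the Schedule of Activities; the illustrative path and the SD ratio rest on the assumptions stated with them.

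**What to change.** Choose one of two wordings for limb (a) in Section 8.3.3:

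1. Any postdose QTcF at least 60 ms above the triplicate-mean baseline and above 450 ms.
2. A single postdose QTcF meeting those limits prompts two further ECGs about 5 minutes apart, and the mean of the three is tested against (a).

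The two are not equivalent. The first is simpler but noisier and drops any element of persistence. The second stays closer to the present wording, but on Days 3 to 5 the participant would have to take the extra tracings at home. Keep the qualified-provider waiver in either case.

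The cost is a change to protocol wording, with no extra scheduled ECGs and no change to the SAP. The downside is a few more repeat ECGs in flagged cases.

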8.3.4. Clinical Safety Laboratory Assessments

See Appendix 2 for the list of clinical safety laboratory tests to be performed and the SoA for the timing and frequency. All protocol-required laboratory assessments, as defined in Appendix 2, must be conducted in accordance with the laboratory manual and the SoA. Unscheduled clinical laboratory measurements may be obtained at any time during the study to assess any perceived safety issues.

The investigator must review the laboratory report, document this review, and record any clinically significant changes occurring during the study in the AE section of the CRF. Clinically significant abnormal laboratory test findings are those that are not associated with the underlying disease, unless judged by the investigator to be more severe than expected for the participant's condition.

All laboratory tests with values considered clinically significant and abnormal during participation in the study or within 28 days after the last dose of study intervention should be repeated until the values return to normal or baseline or are no longer considered clinically significant by the investigator or study medical monitor.

If such values do not return to normal/baseline within a period of time judged reasonable by the investigator, the etiology should be identified and the sponsor notified.

See Appendix 5 for suggested actions and follow-up assessments in the event of potential DILI.

See Appendix 6 for instructions for laboratory testing to monitor kidney function and reporting laboratory test abnormalities.

Participants may undergo random urine drug testing at the discretion of the investigator. Drug testing conducted prior to dosing must be negative for participants to receive study intervention.

8.3.5. COVID-19 Specific Assessments

Participants will be tested for COVID-19 infection by PCR according to local procedure.

8.3.6. Pregnancy Testing

A urine or serum pregnancy test is required at screening. Following screening, pregnancy tests may be urine or serum tests, and must have a sensitivity of at least 25 mIU/mL. Pregnancy tests will be performed in WOCBP at the times listed in the SoA. Following a negative pregnancy test result at screening, appropriate contraception must be commenced and a second negative pregnancy test result will be required at the baseline visit prior to starting the study intervention. Pregnancy tests will also be done whenever 1 menstrual cycle is missed during the active treatment period (or when potential pregnancy is otherwise suspected) and at the end of the study. Pregnancy tests may also be repeated if requested by IRBs/ECs or if required by local regulations. If a urine test cannot be confirmed as negative (eg, an ambiguous result), a serum pregnancy test is required. In such cases, the participant must be excluded if the serum pregnancy result is positive.

8.4. Adverse Events, Serious Adverse Events, and Other Safety Reporting

The definitions of an AE and an SAE can be found in Appendix 3.

AEs may arise from symptoms or other complaints reported to the investigator by the participant (or, when appropriate, by a caregiver, surrogate, or the participant's legally authorized representative), or they may arise from clinical findings of the investigator or other healthcare providers (clinical signs, test results, etc).

The investigator and any qualified designees are responsible for detecting, documenting, and recording events that meet the definition of an AE or SAE and remain responsible to pursue and obtain adequate information both to determine the outcome and to assess whether the event meets the criteria for classification as an SAE or caused the participant to discontinue the study intervention (see Section 7.1).

During the active collection period as described in Section 8.4.1, each participant will be questioned about the occurrence of AEs in a nonleading manner on the days they are at the CRU and they will record the AEs on the CRF during remote participation in the study.

In addition, the investigator may be requested by Pfizer Safety to obtain specific follow-up information in an expedited fashion.

8.4.1. Time Period and Frequency for Collecting AE and SAE Information

The time period for actively eliciting and collecting AEs and SAEs ("active collection period") for each participant begins from the time the participant provides informed consent, which is obtained before undergoing any study-related procedure and/or receiving study intervention), through and including a minimum of 28 calendar days after the last administration of the study intervention.

Follow-up by the investigator continues throughout the active collection period and until the AE or SAE or its sequelae resolve or stabilize at a level acceptable to the investigator.

When a clinically important AE remains ongoing at the end of the active collection period, follow-up by the investigator continues until the AE or SAE or its sequelae resolve or stabilize at a level acceptable to the investigator and Pfizer concurs with that assessment.

For participants who are screen failures, the active collection period ends when screen failure status is determined.

If the participant withdraws from the study and also withdraws consent for the collection of future information, the active collection period ends when consent is withdrawn.

If a participant permanently discontinues or temporarily discontinues study intervention because of an AE or SAE, the AE or SAE must be recorded on the CRF and the SAE reported using the CT SAE Report Form.

Investigators are not obligated to actively seek information on AEs or SAEs after the participant has concluded study participation. However, if the investigator learns of any SAE, including a death, at any time after a participant has completed the study, and they consider the event to be reasonably related to the study intervention, the investigator must promptly report the SAE to Pfizer using the CT SAE Report Form.

